10.1.2 Tables

A table [Study Medication Duration](#) presents for subjects on adjunctive therapy and for subjects on monotherapy, separately:

- Summary statistics on study medication duration

A table [Study Medication Administration](#) presents for subjects on adjunctive therapy and for subjects on monotherapy, separately:

- Summary statistics on mean daily dose and modal dose of study medication

10.1.3 Listings

A subject data listing [Exposure to Study Medication](#) presents for subjects on adjunctive therapy and for subjects on monotherapy, separately:

- Age Category
- Site/Subject Number
- Period
- Date of First Dose
- Date of Last Dose
- Study Medication Duration (days)
- Mean daily dose

10.2 Adverse Events

An overview of AEs presents number and percent of subjects with any TEAE, serious TEAEs, TEAEs leading to discontinuation, TEAEs requiring dose change, any drug-related TEAEs, severe TEAEs, as well as deaths together with the number of individual occurrences in those categories.

Incidences of TEAEs by SOC and PT are presented together with the number of individual occurrences for , TEAEs, , serious TEAEs and serious drug-related TEAEs, and TEAEs leading to discontinuation of study drug.

Additional tables are presented for TEAEs by intensity and for a subset of TEAEs occurring in at least 5% of subjects.

Secondary safety variables for the First Period are: Incidence of TEAEs, Incidence of SAEs, and Incidence of TEAEs leading to discontinuation

Secondary safety variables for the combined First and Second Periods are: Incidence of TEAEs during the combined First and Second Periods, Incidence of SAEs during the combined First and Second Periods, and Incidence of TEAEs leading to discontinuation during the combined First and Second Periods.

Presentations are done for subjects on adjunctive therapy and for subjects on monotherapy, separately.

Subject data listings also cover the verbatim term and further details like start and end date, if applicable.

10.2.1 Definitions and Derivations

The treatment-emergent adverse events (TEAEs) are defined as those events that started on or after the date (and time) of first dose of study medication, or adverse events whose intensity worsened on or after the date (and time) of first dose of study medication.

Adverse events will be coded using the Medical Dictionary for Regulatory Activities (MedDRA®).

10.2.1.1 Categorization of AEs

Adverse events are categorized as pre-treatment and treatment-emergent:

- Pre-treatment: Onset date before first dose of study medication
- Treatment-emergent: Onset date (including severity-worsening) on or after first dose of study medication

10.2.1.2 Assignment of AEs to Periods/Onset of AEs

An AE is assigned to that study period the subject is in during onset of the AE. For the definitions of study periods see [Section 2.3.1](#).

10.2.1.3 AEs Leading to Discontinuation

AEs leading to discontinuation are identified using information documented on the AE CRF.

Both of the following needs to be documented for an event being classified as leading to discontinuation:

- Item “Action Taken with Study Medication” is specified as “Drug permanently withdrawn”
- Item “Did Adverse Event Lead to Dropout?” is specified with “Yes”

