6.3.1 Potential drug-induced liver injury IMP discontinuation criteria

Subjects with potential drug-induced liver injury (PDILI) must be assessed to determine if IMP must be discontinued. In addition, all concomitant medications and herbal supplements that are not medically necessary should also be discontinued.

The PDILI criteria below require immediate and permanent discontinuation of IMP:

- Subjects with either of the following:
 - ALT or AST ≥ 5 xULN
 - ALT or AST ≥ 3 xULN and coexisting total bilirubin ≥ 2 xULN

The PDILI criterion below requires immediate discontinuation of IMP:

- Subjects with ALT or AST ≥ 3 xULN who exhibit temporally associated symptoms of hepatitis or hypersensitivity. Hepatitis symptoms include fatigue, nausea, vomiting, right upper quadrant pain or tenderness. Hypersensitivity symptoms include fever (without clear alternative cause), rash, or eosinophilia (ie, $>5\%$).

The PDILI criterion below allows for subjects to continue on IMP at the discretion of the investigator.

- Subjects with ALT or AST $\geq 3 \times \text{ULN}$ (and $\geq 2 \times$ baseline) and $< 5 \times \text{ULN}$, total bilirubin $< 2 \times \text{ULN}$, and no eosinophilia (ie, $\leq 5\%$), with no fever, rash, or symptoms of hepatitis (eg, fatigue, nausea, vomiting, right upper quadrant pain or tenderness).

Evaluation of PDILI must be initiated as described in Section 11.2.1. If subjects are unable to comply with the applicable monitoring schedule, IMP must be discontinued immediately.

Investigators should attempt to obtain information on subjects in the case of IMP discontinuation to complete the final evaluation. Subjects with PDILI should not be withdrawn from the study until investigation and monitoring are complete. All results of these evaluations and observations, as well as the reason(s) for IMP discontinuation and subject withdrawal (if applicable), must be recorded in the source documents. The CRF must document the primary reason for IMP discontinuation.

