2.2.3.2 Secondary Safety Variables

The secondary safety variables for the First Period are the following:

- Incidence of treatment-emergent adverse events (TEAEs)
- Incidence of serious adverse events (SAEs)
- Incidence of TEAEs leading to discontinuation from study medication

The secondary safety variables for the combined First and Second Periods are the following:

- Incidence of TEAEs
- Incidence of SAEs
- Incidence of TEAEs leading to discontinuation from study medication

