10.2.2 Tables

Tables will be presented for subjects on adjunctive therapy and for subjects on monotherapy, separately.

AE Summaries

For the First Period all TEAE summaries will be presented for all age categories combined on the SS_A and SS_M.

For the combined First and Second Period all TEAE summaries will be presented for all age categories combined on the SS_A and SS_M.

The following summaries will be produced, for the First, and for the combined First and Second Periods):

- Number and percent of subjects with AEs – Overview.
Overview of the Incidence of AEs will include all subjects with at least one TEAE, serious TEAEs, subject discontinuations due to TEAEs, drug-related TEAEs, severe TEAEs, and all deaths (AEs leading to death).
- Incidence of AEs – Overview
- Number and percent of subjects with TEAEs, and Incidence of TEAEs
- Number and percent of subjects with serious TEAEs, and Incidence of serious TEAEs
- Number and percent of subjects with TEAEs by relationship to study medication, and Incidence of TEAEs by relationship to study medication
- Number and percent of subjects with serious TEAEs by relationship to study medication, and Incidence of serious TEAEs by relationship to study medication
- Number and percent of subjects with serious drug-related TEAE
- Number and percent of subjects with TEAEs by Intensity, and Incidence of TEAEs by Intensity
- Number and percent of subjects with serious TEAEs occurring in at least 5% of the subjects, and Incidence of serious TEAEs occurring in at least 5% of the subjects
- Number and percent of subjects with TEAEs leading to (permanent) discontinuation of study medication

Note: permanent discontinuation: when in the Adverse Event CRF the item “Action taken with study Medication” is answered with “Drug Permanently Withdrawn”. And Incidence of TEAEs leading to (permanent) discontinuation of study medication

AEs will be summarized by MedDRA SOC and MedDRA PT. The number and percentage of subjects experiencing each event at least once will be summarized.

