10.2.3 Listings

A listing TEAE Glossary represents the mapping of reported terms to preferred terms and system organ class based on the MedDRA coding dictionary:

- System Organ Class
- Preferred Term
- Reported Term

A subject data listing All Adverse Events presents for subjects on adjunctive therapy and for subjects on monotherapy, separately:

- Age Category
- Region/Country/Site/Subject Number
- Gender/Age/Race/Weight
- System Organ Class/Preferred Term/Reported Term
- AE Onset Date (Relative Day)/AE Outcome Date (Relative Day)/Period
- AE Duration/Dose at Onset/Days on Dose at Onset/Total Days on Treatment
- Seriousness/Intensity
- Pattern of Event
- AE Led to Dropout?
- Relationship to Study Medication/Action Taken with Study Medication/Other Action Taken / AE Outcome

The listing is repeated for:

- Treatment Emergent AEs Leading to Discontinuation
- Deaths and Other Serious TEAEs

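### SAP 10.2.1.3 adds a study-dropout condition to AEs leading to discontinuation, although the secondary safety variable is discontinuation from study medication and the note to the 10.2.2 table uses drug withdrawal alone

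*SAP*

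**What the plan says.** Protocol 4.3.2.1 and 4.3.2.2 and SAP 2.2.3.2 name the same secondary safety variable for the First Period and for the combined periods: "Incidence of TEAEs leading to discontinuation from study medication".

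The rest of the SAP treats the term in several ways:

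- **SAP 10.2.1.3 (general definition).** "Both of the following needs to be documented for an event being classified as leading to discontinuation": the action-taken item must show permanent withdrawal of the drug, and the dropout item must be Yes.
- **SAP 10.2.2 (table of TEAEs leading to permanent discontinuation of study medication).** The note opens "Note: permanent discontinuation: when in the Adverse Event CRF the item" and goes on to name the action-taken item answered with permanent withdrawal. The dropout item is not mentioned.
- **SAP 10.2.2 (AE overview).** The row appears among "serious TEAEs, subject discontinuations due to TEAEs, drug-related TEAEs, severe TEAEs" and has no rule of its own.
- **SAP 10.2.3 (listing).** The output "Treatment Emergent AEs Leading to Discontinuation" also has no rule of its own.
- **SAP 10.2 (restated variable).** "Secondary safety variables for the First Period are: Incidence of TEAEs, Incidence of SAEs, and Incidence of TEAEs leading to discontinuation". The reference to study medication is gone, which leaves the term that 10.2.1.3 defines. The same section does mention study drug when it describes the output by system organ class and preferred term.

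SAP 13 (EudraCT table) also uses AEs leading to discontinuation. It covers the Enrolled Set and all AEs rather than TEAEs, and it does not say which meaning applies.

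**The concern.** Stopping the drug and leaving the study are different events, and the declared variable is about the first. A rule that requires both can miss a subject who stopped the drug permanently because of an AE but is not recorded as a dropout. Any such error lowers the count, which is the unfavourable direction for a safety variable.

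Both rules are in the current text and neither refers to the other. Two programmers could apply different rules in good faith, and one report could then show different subjects under similar labels. This is one of three secondary safety variables in each period.

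**Working it through.** No figure in the plan (sample size, power or alpha) depends on this point, so there is nothing to reproduce. The check compares the rules as sets.

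**Definitions, counted in subjects**

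- A: at least one TEAE with the drug permanently withdrawn. This is the declared variable and the literal content of the 10.2.2 note.
- C: at least one TEAE with the drug permanently withdrawn and the dropout item Yes. This is SAP 10.2.1.3.
- d = |A| − |C|. C is a subset of A, so d ≥ 0.

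**Two readings of the 10.2.2 note**

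| Output | Note is the table's own rule | Note only explains the word permanent |
|---|---|---|
| Overview row (10.2.2) | C | C |
| Listing (10.2.3) | C | C |
| Discontinuation table (10.2.2) | A | C |
| Declared variable (2.2.3.2) | A | A |

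The overview row and the listing are placed under C because 10.2.1.3 is the only general definition; the SAP does not say so outright. On the first reading the outputs can differ from each other by d. On the second they agree with each other, but all can fall short of the declared variable by d.

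**Can d exceed zero?**

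1. Protocol 6.3.1 states "The PDILI criteria below require immediate and permanent discontinuation of IMP". It then states "Subjects with PDILI should not be withdrawn from the study until investigation and monitoring are complete", and it asks for the reason for withdrawal only where withdrawal applies. A subject can therefore be permanently off drug and still in the study.
2. Protocol 11.2.1.4 gives the monitoring no fixed end, and SAP 4.3 plans two data cut-offs. A cut-off can fall between the drug stop and the withdrawal.
3. Protocol 1 treats subjects still in the study at approval as having completed it. A subject off drug but still monitored on that date might never be recorded as a dropout.

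The case is reachable, but mostly temporary. The documents do not show how often it would arise. Whether the two items can still disagree after data cleaning, and how stops made through down-titration are coded, depends on the eCRF Completion Guidelines cited in Protocol 11.1.2.1, which are not available here.

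**Illustrative scale**

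The gap in percentage points is 100 × d / N. The value 38 is the planned number for the primary efficacy analysis, used here as an assumed adjunctive Safety Set. The range 30 to 45 is also assumed. The planned number of monotherapy subjects is 10.

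| d | N = 38 | N = 30 to 45 | N = 10 (monotherapy) |
|---|---|---|---|
| 0 | 0 | 0 | 0 |
| 1 | 1/38 = 2.6 | 1/30 = 3.3 to 1/45 = 2.2 | 1/10 = 10 |
| 2 | 2/38 = 5.3 | 2/30 = 6.7 to 2/45 = 4.4 | 2/10 = 20 |

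**The case against.** The strongest reply is that the output whose label matches the secondary variable is the 10.2.2 table, and its note already uses drug withdrawal alone. On that reading the variable itself is reported correctly. Only the overview row and the listing differ, and the overview label, which speaks of subject discontinuations, suits a dropout condition. Alternatively, the note merely explains a word in the table title, 10.2.1.3 governs everything, and the outputs do not conflict.

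Each reply is fair, but they cannot both be used. The first leaves a listing and an overview row that can disagree with the table. The second removes the disagreement by applying a dropout condition to a variable that does not contain one.

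The remaining replies concern weight, and they largely stand:

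- Protocol 7.2 sends early discontinuations to down-titration and safety follow-up, so there is no planned long-term follow-up off drug.
- SAP 3.4 provides for query resolution and agreement of data handling rules before lock.
- The All Adverse Events listing in SAP 10.2.3 shows both items, so a discordant case can be found and recounted.
- SAP 5.1.2 already tabulates study discontinuation by primary reason, so a new dropout row in the AE overview is not needed.

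A reader might infer that the discontinuation incidence will be understated, or that the outputs are bound to disagree. The documents support neither. They show that an undercount is possible under a stated rule, with a number of affected subjects that may be zero.

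**Conclusion.** The point holds as a defect of definition with minor impact. SAP 10.2.1.3 does not match the declared variable, and the 10.2.2 note does not resolve this on either reading. Where 10.2.1.3 governs, the count can only be equal or lower.

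The number of discordant subjects cannot be derived from the documents. The percentage-point figures show what one or two such subjects would mean and are not an expected effect. No test, threshold or analysis set depends on this variable.

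The conclusion assumes that outputs without their own rule follow the general definition, and that the eCRF conventions, which are not in the documents, do not force the two items to agree.

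**What to change.** Replace the rule in SAP 10.2.1.3 with: *An AE is classified as leading to discontinuation from study medication if the action taken with study medication is Drug permanently withdrawn, regardless of the dropout item.* The sentence should say AE, not TEAE, so that it can also serve the Section 13 table, which uses all AEs.

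Use this definition and label in the AE overview row, the 10.2.2 table (restricted to TEAEs) and the 10.2.3 listing, and restore the reference to study medication where SAP 10.2 restates the variable.

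If a dropout-based output is wanted, define it separately as AE leading to study dropout, based on the dropout item being Yes. It would also show AE-related dropouts coded with another action, which both current rules miss. State which of the two definitions the Section 13 table uses.

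The cost is one sentence and a few labels. No new data are needed, because both items are on the AE CRF. The 10.2.2 table does not change if it already follows its note; otherwise its count, like those of the overview and listing, can only stay the same or rise.

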10.2.1.4 Drug related AE

A drug-related TEAE is defined as any TEAE with “Relationship to Study Medication” recorded as “related” on the CRF as assessed by the investigator or with missing assessment of the causal relationship.

10.2.1.5 Dose at AE Onset

As a conservative approach, in case an AE has onset date on a day with 2 different total daily doses, the lower dose is used.

10.2.1.6 Incomplete Dates

Data handling rules for management of missing or partial start or stop dates for adverse events should follow those defined in the [Section 4.2.3](#).

10.2.2 Tables

Tables will be presented for subjects on adjunctive therapy and for subjects on monotherapy, separately.

AE Summaries

For the First Period all TEAE summaries will be presented for all age categories combined on the SS_A and SS_M.

For the combined First and Second Period all TEAE summaries will be presented for all age categories combined on the SS_A and SS_M.

The following summaries will be produced, for the First, and for the combined First and Second Periods):

- Number and percent of subjects with AEs – Overview.
Overview of the Incidence of AEs will include all subjects with at least one TEAE, serious TEAEs, subject discontinuations due to TEAEs, drug-related TEAEs, severe TEAEs, and all deaths (AEs leading to death).
- Incidence of AEs – Overview
- Number and percent of subjects with TEAEs, and Incidence of TEAEs
- Number and percent of subjects with serious TEAEs, and Incidence of serious TEAEs
- Number and percent of subjects with TEAEs by relationship to study medication, and Incidence of TEAEs by relationship to study medication
- Number and percent of subjects with serious TEAEs by relationship to study medication, and Incidence of serious TEAEs by relationship to study medication
- Number and percent of subjects with serious drug-related TEAE
- Number and percent of subjects with TEAEs by Intensity, and Incidence of TEAEs by Intensity
- Number and percent of subjects with serious TEAEs occurring in at least 5% of the subjects, and Incidence of serious TEAEs occurring in at least 5% of the subjects
- Number and percent of subjects with TEAEs leading to (permanent) discontinuation of study medication

Note: permanent discontinuation: when in the Adverse Event CRF the item “Action taken with study Medication” is answered with “Drug Permanently Withdrawn”. And Incidence of TEAEs leading to (permanent) discontinuation of study medication

AEs will be summarized by MedDRA SOC and MedDRA PT. The number and percentage of subjects experiencing each event at least once will be summarized.

10.2.3 Listings

A listing TEAE Glossary represents the mapping of reported terms to preferred terms and system organ class based on the MedDRA coding dictionary:

- System Organ Class
- Preferred Term
- Reported Term

A subject data listing All Adverse Events presents for subjects on adjunctive therapy and for subjects on monotherapy, separately:

- Age Category
- Region/Country/Site/Subject Number
- Gender/Age/Race/Weight
- System Organ Class/Preferred Term/Reported Term
- AE Onset Date (Relative Day)/AE Outcome Date (Relative Day)/Period
- AE Duration/Dose at Onset/Days on Dose at Onset/Total Days on Treatment
- Seriousness/Intensity
- Pattern of Event
- AE Led to Dropout?
- Relationship to Study Medication/Action Taken with Study Medication/Other Action Taken / AE Outcome

The listing is repeated for:

- Treatment Emergent AEs Leading to Discontinuation
- Deaths and Other Serious TEAEs

10.3 Clinical Laboratory Evaluations

All laboratory data summaries will be presented by analysis visit.

Shifts from baseline to end of treatment based on the normal range (ie, low, normal, high, and missing) for each hematology and clinical chemistry lab parameter will be presented.

The number and percentage of subjects with possibly clinically significant treatment-emergent laboratory values (hematology and clinical chemistry) as defined in [Section 12.3.1](#) and [Section 12.3.2](#), respectively, will be summarized. Possibly clinically significant treatment-emergent laboratory values are those that are observed during the defined treatment period at scheduled or unscheduled visits and were not observed at any visit during the Baseline period. A

subject number table will be presented for subjects with laboratory assessments meeting the marked abnormality criteria.

Individual subject data listings present laboratory data including change from Baseline and flags for abnormal and PCS values.

Subjects who meet one or more of the criteria presented in [Appendix 12.3.3](#) for potential drug-induced liver injury (PDILI) at any time-point (from both scheduled and unscheduled visits) will be listed. The listing will display only visits for which at least one of the above criteria was fulfilled for a given subject, and will display all results obtained at that visit for the specified variables. Potential Hy's law cases will be flagged. If applicable, a summary of subjects who met the criteria for PDILI will be presented separately from all relevant data collected.

PDILI laboratory results and additional PDILI information will be listed. If specific PDILI information collected separately is matching to the entries in the standard eCRF pages collected for all subjects, the specific PDILI information will be added to the corresponding listing for the standard eCRF information (eg, lifestyle information is collected for all study subjects, the additional PDILI information for alcohol and illicit drug use will be included in the listings for lifestyle). For information collected on top (eg, family history of PDILI) a new listing will be generated.

10.3.1 Definitions and Derivations

For continuous laboratory variables (hematology and clinical chemistry) summary statistics of actual values and change from Baseline values will be presented.

In tables that are provided by period, percentages are based on the number of subjects who are at risk for a certain period per age category in the respective analysis set. Subjects who entered a period are regarded as "at risk" for this period.

The list of laboratory variables is given in [Section 12.1](#).

10.3.1.1 Blood Sample

Blood samples are analyzed by a central laboratory and data are available electronically including SI units as well as an assessment of abnormality based on normal ranges (eg, high, low; adjusted for age and gender where applicable).

Change from Baseline (see [Section 3.3](#)) is calculated for each post Baseline visit according to the visit schedule including unscheduled visits and for the Last Visit.

A variable representing categories for possibly clinically significant treatment-emergent (PCST) abnormal values is created for selected hematology and blood chemistry parameters ([Table 12-1](#) and [Table 12-2](#)):

- Too low
- Not PCS
- Too high

PCST abnormal values are defined as any treatment emergent laboratory values meeting the criteria (UCB 2012, GUIDANCE DOCUMENT, Clinical and Laboratory Possibly Clinically Significant Treatment Emergent (PCST) Criteria For Clinical Development Programs in TA CNS).

